**SCHEMA**

## 1.0 INTRODUCTION

### 1.1 Research Hypotheses

This Phase I-II study is designed to test the hypotheses that:

- 1) Initial local radiotherapy during anti-CTLA-4 blockade with Ipilimumab treatment is safe and it increases the objective response rate to immune checkpoint blockade (ICB) by the combination of ipilimumab and nivolumab by 20%.
- 2) The immune response can be prospectively monitored among the treated patients.
- 3) Modifications in the stool microbiome of these patients correlates with response to RT+ ICB.

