### Secondary objectives:

- 2.3 To explore whether early changes in TCR repertoire in peripheral blood are associated with response to treatment
- 2.4 To explore if serum markers levels and their changes are associated with response
- 2.5 To explore associations of ORR with changes in the microbiome
- 2.6 To measure progression free survival (PFS) and overall survival (OS).

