### Objective 2.5: To explore associations of ORR with changes in the microbiome

While immune checkpoint blockade results in remarkably prolonged disease control in a subset of patients [58, 59] modulators of this phenotype are not well understood. Accumulating evidence suggests the gut microbiota play a critical role in response to both anti-PD-L1 efficacy and CTLA-4 blockade: two recently published studies by Vetizou *et al.* and Sivan *et al.* demonstrated in mouse models that the gut microbiome critically impacts response to immunotherapy [58, 59]. Remarkably, by altering the composition of commensal microbiota, the response to CTLA-4 blockade and anti-PD-L1 therapy could be manipulated and therapeutic response markedly enhanced. These pre-clinical studies provide strong rationale for our hypothesis that the human gut microbiome composition will correlate with response to ICB and RT. Identification of commensal organisms harbored in patients with heightened antitumor immune response can ultimately be manipulated to achieve desired outcomes in a greater proportion of patients. Fecal transplant is an established clinical technique whereby microbiota can be transferred into humans to induce select therapeutic outcomes, providing direct clinical applicability of any findings [30].

The study by Vetizou *et al.* underscores the dependence of CTLA-4 blockade on commensal microbiota [59]. First, the authors demonstrate that anti-CTLA-4 therapy is ineffective in mice that are housed in germ-free cages or treated with antibiotics.

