By transferring specific gut microbiota back into antibiotic-treated or germ-free mice, the anticancer efficacy of CTLA-4 blockade could be recovered. The transfer of T cells specific to *Bacteroides fragilis*, or immunization with dendritic cells exposed to *B. fragilis* polysaccharides, also restored the antitumor effect of CTLA-4 blockade. Additionally, Vetizou *et al.* explored human gut microbiome changes in 25 malignant melanoma patients treated with CTLA-4 blockade, who at baseline fell into three microbial cluster patterns (Clusters A-C). During treatment, the microbial composition altered, becoming more similar to cluster pattern "C" and distant from cluster pattern "B". Subsequent fecal transplantation from cluster C patients into mice resulted in a significant response to CTLA-4 blockade, whereas transplantation from cluster B patients had no response, providing evidence that host gut microbial composition has a significant impact on likelihood of ICB success.

Sivan *et al.* likewise provides compelling data supporting the importance of gut microbiota in

determining treatment efficacy to ICB [58]. The authors compared growth of melanoma cell lines in two sets of mice harboring distinct gut microbiota, with differential tumor growth and response to PD-L1 therapy, and identified a specific bacterial species, *Bifidobacterium*, to be associated with antitumor immunity. By transferring *Bifidobacterium* from JAX mice to poorly-responding TAC mice, the authors were able to improve baseline anti-tumor immunity, and significantly enhance anti-PD-L1 therapy response. The therapeutic effect of *Bifidobacterium* was established to arise from altered dendritic cell function and increased priming of tumor-specific CD8+ T cells. Only live bacteria could achieve this effect, implying that augmentation of dendritic cell function requires direct interaction of host cells with gut microbiota [30]. These novel findings signify that the gut microbiome composition impacts response to anti-PD-L1 therapy and can be manipulated to enhance treatment response, providing impetus for similar analyses in human subjects.

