Taken together, the above preclinical studies lend strong support towards collection of gut microbiome samples from patients enrolling on all future immunotherapy studies. We propose to collect stool samples from study patients before treatment and at day 21, 3 months and 6 months for analysis of microbiome composition and changes after ICB and RT. Both pre-clinical and clinical data demonstrate that the addition of RT to ICB creates a robust immune response, eliciting anti-tumor immune responses in otherwise non-responding patients. Given that we expect a similar heightened response in our proposed study, our patient cohort with its expected dichotomous outcomes will be particularly suitable for microbiome analysis. The results will be an important step towards understanding, and ultimately harnessing, the interplay between the human gut microbiome and anti-tumor immune response.

**Methods** Stool collection will occur before treatment, at day 22, day 70 and at 6 months follow up to explore changes of the microbiome during ICB. Bacterial diversity and taxonomy will be estimated by high throughput sequencing (HTS) of 16S rRNA amplicons, using the MiSeq platform in the Genomic Technology Core Lab. Methods have been established in the [name] Lab and proven to yield accurate and reproducible results.[60, 61] Analysis will be based on the QIIME (Quantitative Insights into Microbial Ecology) software package developed by the Knight lab, [62] and machine learning analyses developed by NYU Center for Health informatics and Bioinformatics (CHIBI) investigators working on NYU Human Microbiome Program studies [63, 64](64,65). Appendix 10 describes the protocol for stool collection.

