Changes in the gut microbiome will be assessed globally and at each individual timepoint. In the global analysis of measure of diversity, the data will be summarized by a normalized area under the curve (AUC). The AUC of responders will be compared to the AUC of non-responders using a two-group t-test (or non-parametric test if more appropriate). In addition, logistic regression will assess the relationship of the AUC for the diversity index and responder status. This model may adjust for baseline levels of diversity and other relative clinical variables. Changes in the diversity index will also be evaluated at each timepoint and compared between responders and none responders using a two-group t-test (or non-parametric test if needed). A similar analysis will be done with the changes in serum marker levels over time. A global analysis will be done using a normalized AUC and making a comparison between responders and non-responders. There will also be analyses done for changes at each timepoint between responders and non-responders. For these analysis, we will also generate graphs of the data that show the changes over time in the measurements for each individual patient (i.e. a spaghetti plot). We will superimpose a loess curves on the plot: one for the entire cohort, one for responders and one for non-responders). Given the relatively small sample size, these analyses are exploratory and no adjustment will be made for multiple comparisons.

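### Section 17.3 tests the microbiome objective only through a diversity index, so composition differences that leave diversity about unchanged would be missed and no organism could be identified

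*Combined protocol and SAP*

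**What the plan says.** The hypothesis appears at three levels of detail.

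- Section 1.1 puts it broadly: "Modifications in the stool microbiome of these patients correlates with response to RT+ ICB".
- Section 3.0 lists the secondary objective as "To explore associations of ORR with changes in the microbiome".
- The rationale for Objective 2.5 in section 4.0 is more specific. It refers to "our hypothesis that the human gut microbiome composition will correlate with response to ICB and RT", and it has an organism-level aim: "Identification of commensal organisms harbored in patients with heightened antitumor immune response can ultimately be manipulated".

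The Methods paragraph of Objective 2.5 plans the measurement: "Bacterial diversity and taxonomy will be estimated by high throughput sequencing (HTS) of 16S rRNA amplicons". It names QIIME and machine learning as tools, with stool taken before treatment, at Day 22, at Day 70 and at 6 months. It gives no comparison of taxonomy with response.

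Section 17.3, Secondary analyses, gives the tests. Responders and non-responders are compared on a normalised area under the curve (AUC) of a diversity measure. Responder status is then regressed on that AUC in a logistic model. Finally, "Changes in the diversity index will also be evaluated at each timepoint and compared between responders and none responders using a two-group t-test", with a non-parametric alternative. The index is not named. The section calls these analyses exploratory because the sample is small, and makes no multiplicity adjustment.

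**The concern.** The quantity tested is narrower than the quantity hypothesised. Composition is a profile of many taxa, while a diversity index reduces that profile to one number that does not record which taxa make it up. Responders and non-responders could carry clearly different bacteria at similar diversity, and none of the specified tests would be expected to show it. Even a positive diversity result would not say which organisms differ, and identifying organisms is the aim in the Objective 2.5 rationale.

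Two things are at stake. A null diversity result could be read as no microbiome association when much of the hypothesis had not been examined. And any taxon-level result reported later would have been picked from many taxa with no planned analysis and no error control.

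**Working it through.** The documents give no alpha, power or effect size for the microbiome tests, so there is no figure to reproduce. The check sets the tests against the hypothesis and then illustrates the consequence.

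**1. What each specified test uses (section 17.3, Secondary analyses)**

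| Test | Quantity | Depends on which taxa are present? |
|---|---|---|
| Responders vs non-responders, global | Normalised AUC of a diversity measure | No |
| Logistic regression of responder status | AUC of the diversity index | No |
| Responders vs non-responders, each timepoint | Change in the diversity index | No |

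An AUC over time and an optional adjustment for baseline diversity both need one number per sample. The text therefore cannot be read as a between-sample distance analysis.

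**2. Invariance of the index**

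Take Shannon's index, H = −Σ p·ln p, as the example, since the plan names none. Let two taxa with mean abundance 0.131 and 0.052 exchange places. Their contribution to H is 0.131 × 2.033 + 0.052 × 2.957 = 0.266 + 0.154 = 0.420 before and after, so H is unchanged. The Bray-Curtis distance between the two mean profiles is ½ × (0.079 + 0.079) = 0.079, which is not zero. This invariance is exact for exchanged abundances. It does not extend to composition differences in general.

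**3. Illustrative simulation**

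The 44 evaluable patients come from section 17.2. Everything else is assumed: 18 responders, 20 taxa, Dirichlet-multinomial counts with concentration 30, 10,000 reads, one timepoint, two-sided 0.05, and 500 runs per scenario. The composition test is a permutation multivariate analysis of variance on Bray-Curtis distances with 199 permutations.

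| Scenario | t-test on Shannon | Composition test |
|---|---|---|
| No difference | 0.054 | 0.064 |
| Two taxa exchange abundances (0.131 and 0.052) | 0.038 | 1.00 |
| Loss of rare taxa | 1.00 | 0.984 |
| Bloom of the dominant taxon | 0.976 | 0.998 |

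The Monte Carlo standard error at 0.05 is √(0.05 × 0.95 / 500) = 0.010, so 0.054, 0.064 and 0.038 are all compatible with the nominal level. In the exchange scenario an unadjusted rank test on one affected taxon also rejected in every run.

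A second set of assumptions gives the same pattern for exchanges: 20 vs 24 patients, 60 genera, two genus pairs exchanged (11.7% with 3.9%, and 8.0% with 3.3%), concentrations 20, 40 and 80, 400 runs each. The Shannon t-test rejected in 0.0425, 0.030 and 0.0525 of runs, and the composition test in 1.00 at each setting.

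**4. What a null diversity result would rule out**

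For a two-sided 0.05 t-test with 80% power and an 18 vs 26 split, the normal approximation is d = (1.960 + 0.842) × √(1/18 + 1/26) = 2.802 × 0.307 = 0.86. The exact t calculation gives 0.88. With 14 or 22 responders the exact values are 0.93 and 0.86. Only large diversity differences would be found reliably, so a null result is weak evidence even about diversity.

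**The case against.** The best reply has three parts.

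**Composition is not left out of the protocol.** Objective 2.5 plans taxonomy, names QIIME and machine learning, cites work on classifying microbiome data, and says the cohort's two-way outcome suits microbiome analysis. Some classification of response from microbiome data is therefore signalled. This stands, and it would be wrong to infer that composition is ignored. But no distance, model, comparison with response or validation is stated, and none of it reaches section 17.3. The gap is in the specified analysis, not in the measurement.

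**Diversity is a function of composition.** A reader might infer that the planned tests cannot detect the hypothesised effect at all, or that a diversity difference would say nothing about composition. Neither follows. Groups that differ in diversity must differ in composition, so such a finding would be indirect support for the hypothesis. The simulation shows high rejection when the change also shifts diversity. Only roughly diversity-neutral differences are missed.

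**The objective is exploratory.** No efficacy, safety or stopping decision uses it, and nothing in the documents says that a null diversity result would be reported as no association. This limits the consequence. It does not explain why the specified tests address a different quantity from the one hypothesised.

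A reader might also take the bacteria named in the rationale as the trial's hypothesis. They are not. They appear in the account of cited experiments, such as "By transferring specific gut microbiota back into antibiotic-treated or germ-free mice, the anticancer efficacy of CTLA-4 blockade could be recovered", and no stated hypothesis or objective of this trial names a taxon.

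**Conclusion.** The point holds as a gap between hypothesis and analysis. Section 17.3 specifies microbiome-response tests only on an unnamed diversity index, while Objective 2.5 states a composition hypothesis, aims to identify organisms and collects taxonomy. The planned tests would miss composition differences that leave diversity about unchanged, and they cannot identify organisms. They can detect changes that also alter diversity.

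In the illustration, rejection for a diversity-neutral exchange was 0.04 with the diversity test and 1.00 with a composition test. The sizes rest on assumed abundances and dispersion, and the 1.00 reflects effects large enough to saturate the composition test. Only the pattern carries over. How often real differences between responders and non-responders would be diversity-neutral cannot be judged from the documents.

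This is a cheap improvement to an exploratory secondary objective. The ORR decision does not depend on it.

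**What to change.** In section 17.3, Secondary analyses, keep the diversity analyses, name the index, and add:

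1. A permutation multivariate analysis of variance on Bray-Curtis or UniFrac distances by responder status, at baseline and at Day 22. Both samples precede the Day 70 response assessment. Because the objective concerns changes, add a comparison of within-patient change from baseline to Day 22, for example the distance between each patient's own two samples, compared between groups. That distance measures the size of a change and not its direction, so item 2 should also be run on change.
2. An exploratory taxon-level comparison of responders and non-responders with false discovery rate control. Amend the sentence that rules out multiplicity adjustment for this analysis only.
3. A statement that a null diversity result alone is not evidence of no microbiome association.

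The genera from the cited experiments should not be made into endpoints.

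The cost is a few sentences, slightly more analysis and more exploratory tests to report. The 16S data and QIIME are already planned, and no new samples or patients are needed.

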### **17.4 Study monitoring**

There will be monthly reports generated for study accrual, observed AEs, and data timeliness. The study team will review these reports. In addition, the study will undergo periodic review by the Weill Cornell data safety and monitoring board (DSMB) semi-annually.

### **17.5 DSMB Safety Review**

The protocol will be reviewed by the Data Safety Monitoring Board (DSMB) on a semi-annual basis. Safety reports will be submitted to the DSMB every six months.

## **ADMINISTRATIVE SECTION**

### **Compliance with the Protocol and Protocol Revisions**

The study will be conducted as described in the final approved protocol. Documentation of approval signed by the chairperson or designee of the IRB(s) will be sent to the WCM protocol manager.

All revisions (protocol amendments, administrative letters, and changes to the informed consent) will be submitted to the WCM protocol manager. The Investigator will not implement any deviation or change to the protocol without prior review and documented approval/favorable opinion from the IRB of an Amendment, except where necessary to eliminate an immediate hazard(s) to study patients.

Subsite:

All sub sites will follow local institutional guidelines to manage the study locally. All regulatory requirements will be governed by the local institutional guidelines.

## **18.0 INFORMED CONSENT**

The Investigator will ensure that patients are clearly and fully informed about the purpose, potential risks, and other critical issues regarding clinical trials in which they volunteer to participate. Preparation of the consent form is the responsibility of the Investigator and will include all elements required by the Code of Federal Regulations 21 Part 50.25 and the local IRB. Written informed consent will be obtained by physicians and nurse practitioners listed on the title page of this protocol. The informed consent form will be signed by the subject and the registering physician. Once signed, a copy will be given to the subject and one will be maintained with the subject's medical record. Once eligibility is confirmed and informed consent is documented, the patient will be registered by the study coordinator/data manager. In this protocol, blood and biopsies will be procured and stored with barcoded identifiers. The study samples obtained will be for the purpose of immune-monitoring study when funds become available.

### **18.1 Records and Reports**

Adequate and accurate case histories designed to record all observations and other data pertinent to the investigation (e.g., case report form) will be prepared and maintained on each individual treated with ipilimumab. The investigator will retain, in a confidential manner, the data pertinent to the study.

## **18.2 Records Retention**

The Investigator will retain source documents, and case histories designed to record all observations and other data pertinent to the investigation (e.g., case report form) for the maximum period required by applicable regulations and guidelines, or Institution procedures.

If the Investigator withdraws from the study (e.g., relocation, retirement), the records shall be transferred to a mutually agreed upon designee (e.g., another Investigator, IRB). Documentation of such transfer will be provided to WCM.

## **18.3 Laboratory Correlative Studies**

Serial blood samples for immune monitoring, Genomics and T-cell response will be collected at baseline, and at selected time points as outlined in Section 3.1 and Appendix 2.

Approximately 4-6 mm of tissue will be obtained from four Core punch biopsies will be performed at baseline and at end of treatment.

### **Sub-sites:**

Samples collected at sub sites will be shipped directly to the WCM via overnight shipping. We request that the sites notify the WCMC research team regarding number of patient samples being shipped and the tracking number of the specimens. Please refer to Appendix 1 for more information.

## **18.4 Storage of Samples**

All blood and tissue samples will be processed immediately and stored indefinitely for later analysis in a locked -80°C freezer in the WCM, Radiation Biology Division Biorepository for research purposes only. These specimens will not be linked to any clinical data and will be de-identified in the clinical research database, Redcaps. Only the data manager will have access to the master list with the patient name and an identification number. This master list will be secured in a locked cabinet at the Clinical trials office of the Department of Radiation Oncology (located in W2). Only the investigators listed on this protocol will have access to these samples. After both blood and tissue samples are analyzed at a later date, any unutilized samples will be preserved indefinitely in the WCM Biorepository for potential future research.

All patients enrolled will be given a unique identifier (study ID number). Only the data manager will know the code linking patient and study ID number. Patients will be assigned a unique code number. All specimens collected will be de-identified and assigned the same unique study number of the corresponding patient and will also be marked with the collection time point. Clinical information regarding toxicities and response will likewise be stored in a de-identified database using only the unique identifier (study ID number).

Serial blood for immune monitoring studies will be collected at baseline, at the end of radiation therapy, at the time of the first three infusions of ipilimumab, at the time of the first three infusions of nivolumab, at response evaluation (day 70), and at 6 month follow up.

Small aliquots of PBMC ( $\sim 10^6$  cells) will be used ex vivo for preparation of DNA and RNA, and the remainder preserved frozen until evaluation by flow cytometry and/or by functional assays. A diagnostic tissue biopsies is obtained at baseline in all patients, as per Standard of Care. Access to this histological specimen is required for the study to establish pre-treatment immunological infiltrate. In patients who consent to a pre and post-treatment biopsy of any irradiated lesions tissue will be acquired before the first radiotherapy and first Ipilimumab treatment and again at 3 weeks in patients who receive RT to an accessible metastasis and consent to these OPTIONAL research biopsy. These blood and tissue samples will be utilized for correlative studies as outlined above (section 3.2, page 24) obtained to perform correlative studies or until subject withdraws consent for banking of study specimens. If consent is withdrawn by the study subject, samples will be destroyed as per standard practices.

The storage of your blood and tissue is optional and you may withdraw your consent for the banking of these specimens at any time. You may make this request by writing to the Principal Investigator [name]. at WCM, [name].

